### **5.2.5 Treatment Beyond Progression**

Accumulating evidence indicates that some patients treated with immunotherapy may derive clinical benefit despite initial evidence of progressive disease. Patients will be permitted to continue on treatment beyond progressive disease as long as they meet the following criteria:

- Investigator-assessed clinical benefit.
- Continue to meet all other study protocol eligibility criteria.
- Patient tolerates study drug(s).
- No clinical signs or symptoms of disease progression or clinical deterioration.
- Patient has stable ECOG performance status of  $\leq 2$ .
- Treatment beyond progression will not delay an imminent intervention to prevent serious complications of disease progression (eg, central nervous system metastases).

The assessment of clinical benefit should take into account whether the patient is clinically deteriorating and unlikely to receive further benefit from continued treatment. All decisions to continue treatment beyond initial progression must be discussed with the Medical Monitor, and an assessment of the risk/benefit of continuing with study drug(s) must be documented in the patient records. Patient will sign a "treatment beyond progression ICF" prior to continuing.

### **5.2.6 Safety Follow-up**

The Safety Follow-up visit should occur 60 days after the last dose of study treatment unless the patient withdraws consent to treat, initiates new anti-cancer therapy, is lost to follow up, or death occurs. In case of a clinically significant AE, the patient will be followed for safety until resolution, return to baseline values, or permanent sequelae of all toxicities attributable to study drug(s). If the patient discontinues study drug for a clinically significant AE, the patient will be followed until resolution of the AE or until the event is considered to be stable and/or chronic.

### **5.2.7 Survival Follow-up**

Following discontinuation of study treatment, patients will be contacted approximately every 3 months  $\pm 14$  days after the EOT by clinic visit or telephone, or other alternate methods such as email, contact with family, or public records (if allowed per local regulations), to obtain the information about alternative anti-cancer therapy and assess survival information until the patient meets the criteria for study discontinuation in Section [5.2.3.3](#).

### **5.2.8 End of Study**

End of study is defined as no more than 2 years after the last patient received his or her last dose of NKTR-255 or Sponsor decision to terminate the study, whichever comes first.

At the conclusion of the study, patients who continue to demonstrate clinical benefit may be able to receive Nektar-supplied study treatment for a maximum treatment duration of 2 years. NKTR-255 may be provided via an extension of the study, a rollover study requiring approval by the responsible health authority and ethics committee, or through another mechanism, at the discretion of Nektar.

Nektar reserves the right to terminate access to Nektar-supplied study treatment if any of the following occur: 1) a study is terminated due to safety concerns; 2) the development of NKTR-255 is terminated for other reasons, including but not limited to, lack of efficacy and/or not meeting the study objective; 3) the patient can obtain medication from a government sponsored or private health program. In all cases Nektar will follow local regulations.

### **5.3 Administration of Study Drug(s)**

#### **5.3.1 NKTR-255 Dosing**

Dose administration is shown in [Figure 2](#) and [Figure 3](#). NKTR-255 will be administered as a 30-minute infusion, q21d as monotherapy and in combination with cetuximab, and q28d as single-agent maintenance at the same dose as the patient's originally assigned dose. For applicable dose levels or cohorts (Phase 1b **CCI** [REDACTED]), cetuximab will be given weekly. **CCI** [REDACTED]  
[REDACTED]

The dose does not need to be recalculated for weight changes that are < 10% from baseline (Day -7).

### 5.3.1.4 NKTR-255 Monotherapy with Cetuximab Add-On

Patients in Cohorts C, D, E, A1, and B1 (monotherapy cohorts) who, after at least 1 tumor assessment, do not experience PR or CR per RECIST 1.1, will have the option to receive cetuximab as “add-on” therapy. Patients opting to receive NKTR-255 in combination with cetuximab will maintain their original cohort assignment.

Patients will receive a loading dose of cetuximab 400 mg/m^2 IV 7 days prior to their next scheduled cycle of NKTR-255 and thereafter cetuximab will be administered at a dose of 250 mg/m^2 IV weekly.

Patients in the “add-on” treatment group will be assessed, monitored, and treated as per [Table 5](#). All other portions of the protocol applicable to patients receiving NKTR-255 in combination with cetuximab are applicable to these cetuximab add-on patients as well.

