#### **3.2 Secondary Objectives**

The secondary objectives are:

- To evaluate the efficacy of NKTR-255 monotherapy in R/R **CCI** by assessing the ORR by RECIST 1.1
- To evaluate the efficacy of NKTR-255 in combination with cetuximab and NKTR-255 monotherapy by assessing progression-free survival (PFS) and overall survival (OS)

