### **9.2 Determination of Sample Size**

This is a Phase 1b/2 dose escalation and dose expansion study. During dose escalation (Phase 1b), successive groups of at least 3 patients will be treated at each dose level until the MTD and/or RP2D is determined. Additional patients may be added to each dose level based on the scheme and rules outlined in Section 5.2.3.4 or Sponsor determination of the need for additional data to further evaluate the benefit/risk profile. It is estimated that approximately 30 patients will be enrolled in the dose escalation.

A Bayesian design will be used CCI [REDACTED].

For HNSCC and CRC cohorts, an initial 12 patients will be enrolled into stage 1 of Cohorts A and B, respectively, and the enrollment will continue to a maximum of 24 patients or until the criteria of  $\text{Pr}(\text{ORR} > 0.25 | \text{Data}) > 30\%$  is met. Patient enrollment to Cohorts A1 and B1 will be gated by the Bayesian criteria. After the initial 5 patients' first tumor assessment, subsequent patients will be randomized to the second stage of Cohort A versus Cohort A1, and the second stage of Cohort B versus Cohort B1 using adaptive randomization.

With adaptive randomization, patients will be adaptively assigned proportional to weighted clinical utility function based on available response data. Higher scores are assigned to better responses: [CR  $\geq$  6m = 6], [CR = 5], [PR  $\geq$  6m = 4], [PR = 3], [stable disease (SD)  $\geq$  6m = 2], [SD = 1], [progressive disease = 0], thus a new patient will have higher chance to be assigned to the cohort with better responses. A minimum of 0.1 allocation probability will be retained for each cohort. A maximum of 50 patients each will be enrolled into Cohort A and Cohort B, and a maximum of 26 patients each will be enrolled into Cohort A1 and Cohort B1.

Prior for ORR is set to be Beta(0.25,0.75) corresponding to a prior belief of ORR = 0.25 with 1 effective sample. The following Bayesian decision rules will be applied to Cohort A, Cohort A1, Cohort B, and Cohort B1, respectively, to guide the Go/No-Go decision:

- Select an arm as superior if

- $\text{Pr}(\text{ORR} > 0.25 | \text{Data}) > 80\%$  and  $\text{Pr}(\text{ORR} > 0.10 | \text{Data}) > 90\%$
- Suspend accrual to an arm if  $\text{Pr}(\text{ORR} \leq 0.10 | \text{Data}) > 85\%$
- Achieve maximum sample size

CCI

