With adaptive randomization, patients will be adaptively assigned proportional to weighted clinical utility function based on available response data. Higher scores are assigned to better responses: [CR  $\geq$  6m = 6], [CR = 5], [PR  $\geq$  6m = 4], [PR = 3], [SD  $\geq$  6m = 2], [SD = 1], [progressive disease = 0], thus a new patient will have higher chance to be assigned to the cohort with better responses. A minimum of 0.1 allocation probability will be retained for each cohort.

CCI

Prior for ORR is set to be Beta(0.25, 0.75) corresponding to a prior belief of ORR = 0.25 with 1 effective sample. The following Bayesian decision rules will be applied to Cohort C, Cohort C1, Cohort D, Cohort D1, Cohort E, and Cohort E1, respectively, to guide the Go/No-Go decision:

- Select an arm as superior if
  - $\text{Pr}(\text{ORR} > 0.25 | \text{Data}) > 80\%$  and  $\text{Pr}(\text{ORR} > 0.10 | \text{Data}) > 90\%$
- Suspend accrual to an arm if  $\text{Pr}(\text{ORR} \leq 0.10 | \text{Data}) > 85\%$
- Achieve maximum sample size

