**Treatment-emergent adverse events (TEAE):**

- Any AE that occurs after study treatment initiation.
- An AE that was present at the time of study treatment initiation but worsened after study treatment initiation.
- An AE that was present and resolved prior to treatment and reappeared after treatment initiation.
- Any treatment-related AE will always be considered treatment-emergent.

**NKTR-255 Treatment-emergent adverse events (TEAE) period:** Start of NKTR-255 through 30 days post last dose NKTR-255, or until a new antineoplastic regimen has been initiated, whichever comes first.

**Extended treatment-emergent adverse events (TEAE) period:** Start of any study drug through 60 days post last dose of study drug, or until a new antineoplastic regimen has been initiated, whichever comes first.

**Prior medications:** Prior medications are defined as medications with start date prior to C1D1.

**Concomitant medications:** Concomitant medications are defined as medications with stop date after C1D1, or medications with start date on or after C1D1 and up to 30 days after the last dose of NKTR-255. Medications with a start date after the initiation of any subsequent anticancer treatment will not be considered concomitant medications.

Medications with start date prior to C1D1 and end date after C1D1 will be classified as both prior and concomitant medications.

**Best overall response (BOR):** The BOR is defined as the confirmed best response designation over post-baseline response assessments. Disease assessments beyond progression or after start of subsequent therapy will not be considered for BOR.

**Overall response rate (ORR):** The ORR is defined as the proportion of subjects who have achieved PR or better as their BOR.

**Complete response rate (CRR):** The CRR is defined as the proportion of subjects who have achieved CR as their BOR.

**Responders:** Responders are defined as subjects with a confirmed BOR of PR or better. Ongoing responders are defined as responders who have not progressed, not died, not been off study and not started a subsequent therapy.

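### The visible Phase 2 plan sets no response cut-off at cetuximab add-on, so read literally a combination response in a patient with stable disease counts toward monotherapy ORR and its Go/No-Go rule

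*Protocol*

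**What the plan says.** Protocol 5.3.1.4 covers monotherapy Cohorts C, D, E, A1 and B1. Patients who, after at least one tumor assessment, "do not experience PR or CR per RECIST 1.1, will have the option to receive cetuximab as “add-on” therapy". It then says: "Patients opting to receive NKTR-255 in combination with cetuximab will maintain their original cohort assignment".

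Protocol 9.2 makes the cohort the unit of decision. For HNSCC and CRC: "The following Bayesian decision rules will be applied to Cohort A, Cohort A1, Cohort B, and Cohort B1, respectively, to guide the Go/No-Go decision". For the other tumor types, the same "rules will be applied to Cohort C, Cohort C1, Cohort D, Cohort D1, Cohort E, and Cohort E1". An arm is selected if Pr(ORR > 0.25) exceeds 80% and Pr(ORR > 0.10) exceeds 90%. Accrual is suspended if Pr(ORR ≤ 0.10) exceeds 85%. Allocation probabilities use a response score: 1 for stable disease (2 if it lasts at least 6 months), 3 for PR (4 if it lasts at least 6 months), and higher for CR.

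Monotherapy response is an objective in its own right. Protocol 3.2 includes "To evaluate the efficacy of NKTR-255 monotherapy in R/R" disease, with the tumor types redacted; SAP 3.2 names them as cSCC, ASCC and cervical cancer. Protocol 9.6.3 assesses ORR in the Response-evaluable Population (defined in 9.5). Neither section mentions the add-on in its visible text.

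SAP 6.6.1 limits best overall response: "Disease assessments beyond progression or after start of subsequent therapy will not be considered for BOR". SAP 6.6 defines study treatment as either NKTR-255 or cetuximab.

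**The concern.** An estimate of monotherapy response should rest on responses obtained on monotherapy. Here a patient with stable disease can start an active antibody, stay in the monotherapy cohort, continue with scheduled scans and later reach PR. Nothing visible says whether that PR belongs to the monotherapy ORR.

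Three things depend on the answer. The first is the monotherapy ORR itself. The second is the Go/No-Go decision for Cohorts A1, B1, C, D and E: an inactive arm could be selected, or could escape suspension, on responses to the combination. The third is adaptive randomization. A PR after add-on moves a patient's score from 1 or 2 to 3 or 4, which steers later patients toward monotherapy because of what the combination did.

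**Working it through.** **Does any visible rule exclude the response?**

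- Cohort: unchanged by the add-on (Protocol 5.3.1.4).
- Subsequent-therapy exclusion (SAP 6.6.1): not triggered, because cetuximab is study treatment (SAP 6.6). Protocol 8.2 agrees in spirit: for patients who stop treatment, scans end at anti-tumor therapy other than the study treatment.
- Post-progression exclusion (SAP 6.6.1 and 7.5): if applied, it removes responses in patients who progressed before the add-on. It does not touch patients who add cetuximab while in stable disease.

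The open case is therefore the patient with stable disease.

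**The plan's own figure.** The protocol states: "Prior for ORR is set to be Beta(0.25,0.75) corresponding to a prior belief of ORR = 0.25 with 1 effective sample". Check: mean = 0.25/(0.25 + 0.75) = 0.25; effective sample size = 0.25 + 0.75 = 1. Both reproduce.

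**Limits implied by the rules.** Protocol 9.2 caps A1 and B1 at 26 patients each. With x responders, the posterior is Beta(0.25 + x, 0.75 + 26 − x).

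| x of 26 | Pr(ORR > 0.25) | Pr(ORR ≤ 0.10) |
|---|---|---|
| 1 | – | 0.900 |
| 2 | – | 0.687 |
| 8 | 0.723 | – |
| 9 | 0.846 | – |

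At x = 9, Pr(ORR > 0.10) is above 0.99, so the second part of the selection rule is also met. Select at 9 or more; the suspension criterion is met at 1 or fewer.

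**Effect of counting add-on responses.** Let p be the true monotherapy ORR, s the share of all patients who have stable disease and add cetuximab, and q their response rate afterwards. Apparent ORR = p + s × q. None of p, s or q is in the documents. I assume p = 0.10, s = 0.40 (40% with stable disease, all adding cetuximab) and q = 0.20 to 0.25:

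- q = 0.20: 0.10 + 0.40 × 0.20 = 0.18
- q = 0.25: 0.10 + 0.40 × 0.25 = 0.20

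Exact binomial tails with n = 26:

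| ORR seen by the rule | P(X ≥ 9), select | P(X ≤ 1), suspension criterion met |
|---|---|---|
| 0.10 (response frozen at add-on) | 0.0006 | 0.251 |
| 0.18 | 0.033 | 0.039 |
| 0.20 | 0.059 | 0.023 |

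**Range.** Now let f be the share of monotherapy non-responders whose add-on scans count, so that apparent ORR = p + (1 − p) × f × q. The case above has f = 0.40/0.90 = 0.44.

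- f = 0.25, q = 0.10: apparent ORR 0.1225, P(select) 0.3%, P(suspension criterion met) 15.5%.
- f = 0.50, q = 0.25: apparent ORR 0.2125, P(select) 8.2%, P(suspension criterion met) 1.6%.

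All of this is a single look at n = 26, not the sequential operating characteristics of the design.

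**The case against.** **Silence is not a rule.** No sentence says that add-on responses count. Keeping a cohort label does not define a response window, and Protocol 9.1 leaves endpoint definitions to the SAP. Parts of 9.2 and 9.6.3, and Table 5, which governs add-on patients, are redacted, so a cut-off may exist there. This stands: the point is what the visible text permits, not what the sponsor demonstrably intended.

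**Nothing was affected.** SAP 2.0 and 12.0 say that only Phase 1b patients were enrolled and that expansion analyses were removed. The SAP's response rules were therefore written for combination patients, and silence on the add-on is expected there. This also stands, and it limits the point to the Phase 2 design.

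**The numbers are soft.** The rates are assumed. Suspending accrual at the cohort maximum has no practical effect, so that column only shows how the criterion shifts. The cap of 26 belongs to A1 and B1, whereas the monotherapy ORR objective concerns cSCC, ASCC and cervical cancer, for which no maximum is visible. All of this is fair. The direction of the effect on ORR does not depend on these choices.

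**Stronger readings do not hold.** A reader might let every non-responder contribute, including those who progressed. That gives an apparent ORR of 28-32.5% and P(select) of 29-48%, but it contradicts the SAP's post-progression exclusion, the only visible rule on the matter. A reader might also infer that duration of response is biased upward. This is not shown: patients already in response are not offered the add-on. Finally, the rules compare each arm with fixed thresholds, and no formal test of A against A1 is visible.

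**Conclusion.** The concern holds as a gap in the visible Phase 2 plan. Applied as written, the rules credit a response first seen after add-on, in a patient with stable disease, to the monotherapy cohort. If that happens, ORR, the utility score and the select/suspend rules all shift in favor of monotherapy.

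Under the main assumptions the chance of selecting an arm with a 10% response rate stays modest in absolute terms, at 3-6%, but is roughly 50 to 90 times the 0.06% that applies when response is frozen at add-on (0.033/0.0006 to 0.059/0.0006, using unrounded tails). Low uptake or a low add-on response rate makes the effect small.

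The finding is not that any reported monotherapy result is wrong, since none exists. Confidence is moderate because of the redactions. The point matters if the Phase 2 design is used or reused.

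**What to change.** In Protocol 5.3.1.4, 9.2 and 9.6.3, state that in monotherapy cohorts only tumor assessments made before the first add-on cetuximab dose count toward BOR and ORR, the utility score and the select/suspend rules. A patient not in response by then is a non-responder for monotherapy. Report responses after add-on separately, against a scan taken before the add-on.

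Keep PFS and OS in the assigned cohort as the main analysis. Use censoring at add-on only as a sensitivity analysis: patients choose the add-on after failing to respond, so that censoring is likely to be informative.

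The cost is wording. It changes no patient's treatment and needs only the add-on start date. The drawback is a less favorable monotherapy ORR. Because the add-on is possible after one scan, at about week 9, some late responses that monotherapy would have produced will be scored as non-response. If a redacted passage already sets a cut-off, a cross-reference from 5.3.1.4 would be enough.

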### 5.3.1.5 NKTR-255 Dose Delay and Adjustment Criteria

NKTR-255 dose adjustments may only be performed with approval of the Sponsor’s Medical Monitor. Dose adjustments of NKTR-255 within a single patient are not permitted within the DLT window. Outside of the DLT window in the dose escalation phase and during dose expansion, dose levels of NKTR-255 may be reduced depending on the severity, duration, and frequency of toxicities observed at the previous dose level tested (the dose level may be de-escalated in order to characterize RP2D for a specific cohort).

NKTR-255 doses may be delayed or reduced per the recommendation of the Investigator and approval of the Sponsor’s Medical Monitor, based on observed drug-related toxicities for the following reasons:

- Grade 1 or 2 toxicity: No requirement for dose delay or dose reduction. If the toxicity persists at Grade 2 following completion of the cycle, a dose delay or dose reduction may be implemented in consultation with the Medical Monitor.
- Grade 3 toxicity: NKTR-255 may be withheld if toxicity cannot be managed by adequate medical intervention. NKTR-255 dosing may resume at one dose level lower when toxicity resolves to Grade 1 or returns to baseline, except for instances where the potential recurrence of the event poses an undue risk for the patient.
- Grade 4 non-hematological toxicity that is not considered by the Investigator to be attributable to another identifiable cause: dosing should be permanently discontinued.
- For specific severe or medically important toxicities that require permanent treatment discontinuation, refer to Section [5.7](#).

Tumor assessments for all patients should continue as per protocol even if dosing is delayed. Grading of AEs is described in Section 7.3.

#### 5.3.1.6 Criteria to Resume NKTR-255

Patients will be permitted to resume study drug(s) at the same dose level(s) following resolution of the AE to Grade  $\leq 1$  or to baseline within 2 weeks after the completion of the prior cycle, with the exception of patients who meet criteria for permanent discontinuation as specified in Section 5.7.

Patients may resume treatment when the drug-related AE(s) resolve(s) to Grade  $\leq 1$  or baseline, with the following exceptions:

- Patients may resume treatment in the presence of Grade 2 fatigue.
- Patients with baseline Grade 1 AST/ALT or total bilirubin who require dose delays for reasons other than a 2-grade shift in AST/ALT or total bilirubin may resume treatment in the presence of Grade 2 AST/ALT **or** total bilirubin.
- Patients with combined Grade 2 AST/ALT **and** total bilirubin values meeting discontinuation parameters (see Section 5.7) should have treatment permanently discontinued.

A dosing delay lasting more than 2 weeks should be discussed with the Medical Monitor and the patient may resume the study if approved based on clinical assessment.

Tumor assessments should continue as per protocol even if dosing is delayed, and patients must otherwise meet the criteria for continued treatment at the time re-initiation of study therapy is considered.

If the decision is to resume study drug(s) dosing, the patient should restart treatment on the next regularly scheduled study drug(s) dosing visit. Skipped doses are not to be replaced.

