#### **5.5 Dose-Limiting Toxicity Observation Period**

Dose-limiting toxicities will be assessed during the dose escalation and dose expansion portions of the study. The DLT window will be 21 days after the first dose of NKTR-255.

Enrollment into a new dose level with an escalating dose of NKTR-255 may not begin until the DLT window has closed for at least 3 patients in the prior dose level. The dose escalation scheme is described in Section 5.1.

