## 5.7 Permanent Treatment Discontinuation Criteria

Patients meeting any of the following criteria will be required to permanently discontinue all assigned study drug(s). However, with Medical Monitor approval, NKTR-255 treatment may continue if the toxicities listed below are considered related to cetuximab only.

- Progressive disease per RECIST 1.1 (see details regarding continuing treatment beyond initial assessment of progression, Section 5.2.5)
- Clinical deterioration, as assessed by the Investigator
- Grade 3 or 4 CRS (Lee, 2014)
- Grade 3 or 4 IRR
- Grade 4 rash

- Grade 3 laboratory abnormalities require treatment discontinuation for the following:
  - Grade 3 thrombocytopenia  $> 7$  days associated with clinically significant bleeding requires discontinuation.
- Any Grade 4 AE or laboratory abnormality, except for the following events, which do not require discontinuation:
  - Grade 4 neutropenia  $\leq 7$  days
  - Grade 4 lymphopenia or leukopenia
  - Isolated Grade 4 electrolyte imbalances/abnormalities that are not associated with clinical sequelae and are corrected with supplementation/appropriate management within 72 hours of their onset
- Any AE, laboratory abnormality, or intercurrent illness, which, in the judgment of the Investigator, presents a substantial clinical risk to the patient with continued treatment.
- Any dosing delay lasting  $> 2$  weeks after completion of the prior cycle, with the following exceptions (see Section [5.3.1.5](#) for dose delay and adjustment criteria):
  - Patient has not started any new therapy.
  - Dosing delays to allow for prolonged steroid tapers to manage drug-related AEs are allowed. Tumor assessments should continue as per protocol even if dosing is delayed.
  - The Investigator and the Medical Monitor may agree to a longer dose delay following a clinically significant AE if the patient is deriving clinical benefit from the regimen as defined by CR, PR, or stable disease, up to 6 weeks from last dose of either of the 2 investigational agents, per RECIST 1.1. Any delay beyond 6 weeks must be discussed with the Medical Monitor and approval documented.

Tumor assessments should continue as per protocol even if dosing is delayed, and patients must otherwise meet the criteria for continued treatment at the time re-initiation of study therapy is considered (see Section [5.11](#)).

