## **7.6 Safety Analyses**

Unless otherwise specified, all safety analyses except for incidence of DLTs will be based on the Safety Population. All summaries will be provided by dose groups in Phase 1b.

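### For a withheld Grade 3 toxicity that resolves within 2 weeks, Protocol Sections 5.3.1.5 and 5.3.1.6 give different NKTR-255 re-start doses, and no readable text says which governs

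*Protocol*

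**What the plan says.** Two consecutive protocol sections deal with re-starting NKTR-255 after toxicity.

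- **Section 5.3.1.5 (dose delay and adjustment)** works by grade. For drug-related Grade 3 toxicity the drug may be withheld if medical management is not enough, and then "NKTR-255 dosing may resume at one dose level lower when toxicity resolves to Grade 1 or returns to baseline". Events whose recurrence would pose undue risk are excepted. The section also says "NKTR-255 dose adjustments may only be performed with approval of the" Sponsor's Medical Monitor, and "Dose adjustments of NKTR-255 within a single patient are not permitted within the DLT window".
- **Section 5.3.1.6 (criteria to resume)** does not work by grade. It says "Patients will be permitted to resume study drug(s) at the same dose level(s) following resolution of the AE", if resolution is to Grade 1 or less, or to baseline, within 2 weeks after the prior cycle is completed, "with the exception of patients who meet criteria for permanent discontinuation as specified in Section 5.7". For delays beyond 2 weeks it refers the decision to the Medical Monitor and names no dose.

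Section 5.7 lists particular Grade 3 events, for example "Grade 3 or 4 IRR", but not Grade 3 toxicity as such.

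On reporting, SAP Section 7.6 says "All summaries will be provided by dose groups in Phase 1b". SAP Section 7.4.3 summarises cumulative actual dose and the number of patients with dose reductions, and SAP Section 7.6.2 tabulates adverse events leading to NKTR-255 dose reduction.

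**The concern.** A patient whose Grade 3 toxicity caused a hold and then settled promptly meets the conditions of both sections. One describes a lower re-start dose and the other permits the same dose. Neither cites the other.

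The first issue is patient safety: the dose at which someone is re-exposed after a severe drug-related event depends on which section the investigator reads. The second is interpretation. The re-start dose determines what the patient receives in later cycles and whether a dose reduction is counted. It may also affect adverse events and delayed DLTs after the re-start. Protocol Section 5.5.3 has delayed DLTs reviewed when the MTD is determined, and safety and tolerability are among the grounds for choosing the RP2D.

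**Working it through.** There is no plan figure to reproduce. The check sets the sections side by side and traces the consequence.

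**1. Conditions of each rule**

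| | Section 5.3.1.5 | Section 5.3.1.6 |
|---|---|---|
| Event | Drug-related Grade 3, drug withheld | Any AE, no grade limit |
| Resolution | Grade 1 or baseline | Grade 1 or less, or baseline |
| Time limit | None stated | Within 2 weeks after the prior cycle |
| Exceptions | Undue risk on recurrence; Section 5.7 for listed toxicities | Section 5.7 only |
| Approval | Medical Monitor, for delays, reductions and adjustments | None stated for the same-level re-start; Medical Monitor for delays over 2 weeks |
| Re-start dose | One level lower | Same level |

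**2. Does Section 5.7 remove the overlap?** No. Its named Grade 3 events are CRS, IRR, and thrombocytopenia lasting more than 7 days with clinically significant bleeding. It also has general grounds, such as substantial clinical risk in the investigator's judgment. Other Grade 3 toxicities remain. So the overlap is a drug-related Grade 3 toxicity that caused a hold, resolved within the 2 weeks, does not meet Section 5.7 and is not excepted for undue recurrence risk.

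**3. When can it arise?** Section 5.5 says "The DLT window will be 21 days after the first dose of NKTR-255", and NKTR-255 is given every 21 days. Dose adjustment is barred inside the window, so the conflict starts with the re-start for Cycle 2. Section 5.9 estimates the MTD from the probability of DLT in Cycle 1. Cycle 1 DLT incidence and the model input are therefore not directly affected.

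**4. Who may be affected?** Section 5.5.1 makes most related non-hematological events of Grade 3 or higher DLTs, and Section 5.7 does not list a DLT as such as a reason to stop permanently. Patients who have just had a DLT may therefore be among those in the overlap.

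**5. What does it reach in the analysis?** The NKTR-255 treatment-emergent period in SAP Section 6.6.1 runs to 30 days after the last NKTR-255 dose or the start of a new antineoplastic regimen, so it includes resumed cycles. Cumulative dose, dose-reduction counts, treatment-emergent events by dose group and delayed DLTs all draw on those cycles.

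**6. Illustration for one patient, on assumptions.** The dose ladder is redacted. Let k be the doses given before the hold, m the doses after it, and r the lower level divided by the current level. Cumulative dose under the lower-level rule, relative to the same-level rule, is (k + r·m)/(k + m). Section 5.8 limits the model's recommended increase to 100%; if adjacent levels respect that limit, r is at least 1/(1 + 1) = 0.5. Assume k = 2 and m = 4:

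- r = 0.5: (2 + 0.5 × 4)/(2 + 4) = 4/6 = 67%
- r = 0.75: (2 + 0.75 × 4)/(2 + 4) = 5/6 = 83%
- r close to 1: close to 100%

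This shows what the choice can do to one patient's exposure. It does not estimate an effect on the trial.

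**The case against.** The best defence is that the sections can be read together. Both are permissive, so neither compels a dose. Section 5.3.1.5 is specific to grade and to NKTR-255, while Section 5.3.1.6 is general, so a reader could let the specific rule prevail or treat the two as options. The Medical Monitor must approve adjustments, which makes uncontrolled differences between sites less likely. Section 5.7 also points to Section 5.11 for the criteria when treatment is re-initiated, and that section is redacted.

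Much of this stands. The sections do limit their scope, and the overlap is narrower than Grade 3 toxicity in general. But the precedence of specific over general is not written down, the same-level sentence carries no approval step or Grade 3 exclusion, and no criterion for choosing is given.

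A reader might also infer more than the documents support:

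- **That the DLT rate or the MTD estimate is compromised.** The bar on adjustment inside the window and the use of Cycle 1 data for the MTD argue against a direct effect.
- **That patients at the lowest level have no lower dose to go to.** The dose ladder is redacted and intermediate doses are allowed, so this cannot be said.
- **That re-started cycles are reported under the assigned dose.** The readable SAP says dose groups and does not specify assigned or received.
- **That a known share of a dose level is affected.** Level sizes have a minimum but no cap in the readable text, and later-cycle data depend on the cycles each patient receives.
- **That by-dose summaries would be unmixed under one clear rule.** Later reductions are allowed by design, and the SAP's actual-dose and reduction tables make them partly visible.

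**Conclusion.** The inconsistency is real but confined to the overlap set out above. There the protocol offers two re-start doses without a readable rule for choosing. It matters mainly because it governs re-exposure after severe drug-related toxicity, and secondarily because it affects how later-cycle safety and exposure data by dose group are read.

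Its overall size cannot be determined: the documents do not say how many patients would meet the conditions. The 67% to 83% illustration is for a single patient and depends on the assumed dose counts and level spacing. The conclusion also assumes that the redacted text, Section 5.11 in particular, does not already settle precedence. The point is worth correcting but does not call the primary DLT analysis into question.

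**What to change.** Reconcile Sections 5.3.1.5 and 5.3.1.6. State, by toxicity grade, which section governs the NKTR-255 re-start dose, cross-refer each to the other, and say whether a same-level re-start after a Grade 3 toxicity needs Medical Monitor approval. Check the result against Section 5.11. The choice of dose is for the sponsor and investigators; none is proposed here.

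SAP Section 2.0 records that only Phase 1b patients were enrolled, so a protocol correction may have limited forward effect. The SAP or clinical study report should therefore also state whether cycles given at a reduced dose are summarised under the assigned or the received level. For each patient re-started after a Grade 3 hold, it should list the dose before and after.

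The protocol and SAP changes are wording only. The listing is one additional output and should need little or no new data, because actual doses and dose-reduction reasons already feed planned summaries.
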